We will draw upon our working relationships with our various recruitment sites. The randomized controlled trial will be powered on SF-36 change in the patient participant. We used PASS to calculate the minimum detectable score difference required for over 80% power assuming a type I error rate of 0.05. We assumed 50 in each arm. We used the test for two means in a repeated measures ANCOVA. We assumed the correlation between repeated measures to be 0.60 (r2=0.36). The following values were used in the sample size calculations: SF36 Norms Mental Component Summary (MCS): mean = 50; sd = 10 Vitality: mean = 60.9; sd = 21.0 Social Functioning: mean = 83.3; sd = 22.7 Role-Emotional: mean = 81.3; sd = 33.0 Mental Health: mean = 74.7; sd = 18 Table: Minimum detectable score differences Sample Size 50 in each arm MCS 5 Vitality 10 Social Functioning 11 Role-Emotional 15 Mental Health 9 We aim to enroll 115 participants in a randomized controlled trial, with the anticipation that there will be 15% attrition.

Patient Subject Recruitment

We will identify participants across several settings: inpatient and outpatient Penn Medicine clinics (e.g., Emergency Department, Internal Medicine, Center for Cognitive Therapy, PIC, LGH mental health clinics), flyers at [name] and Penn Medicine iConnect (Use of Patient Electronic Communication in Psychiatric Evaluation and Treatment, Study Identifier: 831246), Google ads, Facebook ads, ResearchMatch.org, and provider referrals. Interested patient participants will be directly approached by a research assistant (RA) via email, telephone or BlueJeans. Patients who are receiving care in these settings will receive a digital or printed flyer about the opportunity to participate in a research study. In outpatient units, Ras or AAs will meet regularly with the nursing coordinator, office manager, charge nurse, nurse/ physician team to determine the daily census and appropriateness of approaching patients. If necessary, research assistants will also communicate directly with patients providers (physicians, residents or nurses) to determine whether it is appropriate to approach the patient.

NCT04011540 January 6, 2022

Potentially eligible patients will be approached via email, telephone or BlueJeans to verify they meet all inclusion criteria and will then be asked to participate.

Compensation

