
Amendments to the Statistical Analysis Plan

All amendments to the original SAP were made prior to unblinding of the data analyst and prior to access to outcome data.

Based on covariate balance between the intervention arms, we amended our original statistical analysis plan. In addition, we originally anticipated enrolling 20-30 therapist participants with several patients nested within each therapist. This would have necessitated the accounting for clustering within therapist using random effects. However, we enrolled 69 therapist participants with cluster sizes that were very small, with most therapists treating 1-2 patients. Hence, as our primary analysis, we conducted an unadjusted paired t-test (rather than our originally proposed linear mixed model) to compare mean changes on our primary outcomes from baseline to 60-day. As a secondary analysis, we did conduct a linear mixed effects model exactly as proposed in the original SAP. These results were nearly identical to the unadjusted paired t-test and would not change our conclusions. In addition, we conducted a complete case analysis as our primary analysis. After assessing patterns of missingness and determining that missing at random is a plausible mechanism in this study, we conducted multiple imputation. Again, our imputed results were nearly identical to the complete case analysis with identical conclusions.

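### Enrolling 115 with 15% attrition leaves about 49 per arm, not the assumed 50 (a minor shortfall), and the power table does not describe the amended primary analysis

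*Combined protocol and SAP*

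**What the plan says.** The Accrual section (protocol, Subject Recruitment) holds the only power statement. It reads "We used PASS to calculate the minimum detectable score difference required for over 80% power", "assuming a type I error rate of 0.05", and continues "We assumed 50 in each arm". The method is given as "We used the test for two means in a repeated measures ANCOVA", with a correlation of 0.60 between repeated measures. The tabled differences are MCS 5, Vitality 10, Social Functioning 11, Role-Emotional 15 and Mental Health 9. The section closes with "We aim to enroll 115 participants in a randomized controlled trial, with the anticipation that there will be 15% attrition". It does not show how 115 was obtained.

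The section on amendments to the SAP replaces the mixed model, as primary analysis, with an unadjusted t-test on mean change from baseline to day 60, and adds "we conducted a complete case analysis as our primary analysis". It gives no revised power statement.

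**The concern.** The sequence in the Accrual section implies that 50 per arm is the number left after attrition and that 115 is the enrolment needed to get there. The enrolment and attrition figures leave slightly fewer. With a complete-case primary analysis, patients without day-60 data drop out of that analysis, so attrition reduces the analysed sample directly.

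There is a second mismatch in the same table. Its differences were computed for a baseline-adjusted analysis, and the amended primary analysis does not adjust for baseline. A reader who uses the table to judge what the trial could have detected would be using figures for another sample size and another test.

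**Working it through.** **Inputs, all from Accrual.** SDs: MCS 10, Vitality 21.0, Social Functioning 22.7, Role-Emotional 33.0, Mental Health 18. Correlation r = 0.60, type I error 0.05, 50 per arm, 115 enrolled, 15% attrition. Equal allocation is implied by 50 in each arm and the even block sizes.

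**Step 1: reproduce the table.** With one adjusted follow-up the SD factor is √(1 − 0.60²) = 0.80. The detectable difference is (1.960 + 0.842) × 0.80 × SD × √(2/50), which gives 4.48, 9.41, 10.18, 14.79 and 8.07. By noncentral t (two-sample, 2n − 2 df) the values are 4.53, 9.51, 10.28, 14.94 and 8.15. Either set, rounded up, is the table: 5, 10, 11, 15, 9.

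The plan does not state sidedness. Two-sided is assumed, and it is what fits: one-sided, MCS would be (1.645 + 0.842) × 8 × 0.2 = 3.98, which rounds up to 4, not 5.

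**Step 2: check the enrolment figure.**
- Expected completers: 115 × 0.85 = 97.75, or 48.9 per arm.
- Enrolment that leaves 100: 100/0.85 = 117.6, so 118.
- 100 × 1.15 = 115 exactly, which suggests that the attrition rate was added to the completers rather than taken off the enrolled. This is an inference.
- Attrition that 115 can bear while leaving 100: 1 − 100/115 = 13.0%.

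**Step 3: effect of 49 in place of 50 per arm, and of the amended analysis.** For the change comparison the SD factor is √(2 × (1 − 0.60)) = 0.894. Power (%) for the tabled differences, noncentral t, two-sided 0.05:

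| Scale (difference) | ANCOVA, 50 | ANCOVA, 49 | Change, 50 | Change, 49 |
|---|---|---|---|---|
| MCS (5) | 87.2 | 86.5 | 79.0 | 78.2 |
| Vitality (10) | 83.8 | 83.1 | 75.0 | 74.2 |
| Social Functioning (11) | 85.1 | 84.3 | 76.5 | 75.6 |
| Role-Emotional (15) | 80.3 | 79.5 | 71.1 | 70.2 |
| Mental Health (9) | 87.2 | 86.5 | 79.0 | 78.2 |

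Moving from 50 to 49 costs less than 1 point in every row under either analysis. Moving from ANCOVA to change at 50 per arm costs 8 to 9 points. By normal approximation at 48.9 per arm the ANCOVA powers are 87.1, 83.7, 85.0, 80.2 and 87.1, all above 80%.

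**Step 4: detectable differences at 80% power, 49 per arm (noncentral t).**

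| Scale | Tabled | ANCOVA | Day-60 change |
|---|---|---|---|
| MCS | 5 | 4.6 | 5.1 |
| Vitality | 10 | 9.6 | 10.7 |
| Social Functioning | 11 | 10.4 | 11.6 |
| Role-Emotional | 15 | 15.1 | 16.9 |
| Mental Health | 9 | 8.2 | 9.2 |

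**Step 5: sensitivity of the change comparison to the correlation, 49 per arm.** With r = 0.50 (factor 1.000) power runs from about 61% to 69% across the five scales. With r = 0.70 (factor 0.775) it runs from about 82% to 89%.

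**The case against.** The strongest reply is that the shortfall is immaterial. It is about one patient per arm, the table was rounded up, and four scales stay between 83.1% and 86.5%. The one scale that slips below 80% does so by half a point, and only by noncentral t. The normal approximation keeps it above 80% and reproduces the table equally well. This stands, and it is why the shortfall rates only as minor.

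A second reply is that the primary analysis in the original SAP averaged SF-36 scores over follow-up, with surveys at days 60 and 90. Averaging two follow-ups at correlation 0.60 gives Role-Emotional about 92% at 49 per arm. That is fair for the plan in force when 115 was set. It does not rescue the table, because that method would give a detectable Role-Emotional difference of 12.3 rather than 15. Nor does it apply to the amended primary, which uses day 60 only.

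A third reply is that enrolment and analysis are already reported as done, the plan puts its emphasis on estimates and confidence intervals, and the mixed-model and imputed results are described as nearly identical. This limits what is at stake: no conclusion of the trial turns on the table. It does not make the table describe the analysis used.

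A reader might infer that the target of 115 left the trial underpowered across the board, and might cite 70% to 78% as the result. The documents do not support that. The same change comparison gives 71% to 79% at the full 50 per arm. By normal approximation it needs 51, 56, 54, 61 and 51 per arm for 80%, so enrolling 118 would not have brought any scale to 80%.

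**Conclusion.** The point holds as a minor one, in two parts.

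First, the arithmetic: 50 per arm, 115 enrolled and 15% attrition are inconsistent by about one patient per arm. This is certain from the Accrual figures. Its effect on power is under 1 point per scale, with Role-Emotional borderline at 80%.

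Second, the stated power above 80% belongs to a baseline-adjusted ANCOVA and does not carry over to the amended primary. The size of that gap rests on two assumptions: that the test called paired is a between-arm comparison of change, and that the plan's correlation of 0.60 applies between baseline and day 60. At 0.70 all five scales would exceed 80%. The amendment states neither the test's variance nor its correlation, so the 70% to 79% figures are conditional.

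**What to change.** In Accrual, state that 115 enrolled with 15% attrition is expected to leave about 98 analysed patients (49 per arm), or note that 118 would be needed to leave 100. State that the test is two-sided, if it was.

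Re-issue the detectable differences at 49 per arm for the analysis actually used, naming the test and the correlation assumed: the day-60 change column of the second table above for the amended primary, or the ANCOVA column if a baseline-adjusted analysis is used.

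The cost is one sentence and one table. No extra enrolment is needed. The change-comparison figures are less favourable than the present table, by 0.1 to 0.7 points on four scales and 1.9 points on Role-Emotional. The ANCOVA figures are no worse than the table except on Role-Emotional, by 0.1 point.

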Analysis Plan

Stata, SAS, and NVivo software will be used for analyses. All data will be summarized using descriptive statistics (mean or median, standard deviation, or interquartile range for continuous variables,

NCT04011540 January 6, 2022

frequencies for categorical variables) and graphical techniques (histograms, scatterplot) as appropriate. Standard summary descriptive statistics to be used to analyze data from the survey. We will extract data from social media and wearable device platforms and aggregate to develop dashboards. Qualitative analysis using grounded theory will be applied for the focus group discussion, interviews, and openended survey questions. We will conduct an intent to treat (ITT) analysis. The ITT analysis will include all randomized patients in the groups to which they were randomly assigned, regardless of their adherence with the entry criteria, regardless of the treatment they actually received, and regardless of subsequent withdrawal from treatment or deviation from the protocol. Baseline demographic and clinical characteristics will be reported as frequency and percent for categorical variables and median and interguartile range (IQR) for continuous variables. We will compare baseline characteristics between intervention and control arms using t-tests for continuous variables and chi-squared tests for categorical variables. The goal of these comparisons will be to determine if the two arms are balanced on baseline variables after randomization. For the primary analysis, we will use linear mixed effects models to assess whether average of SF 36 scores over study follow-up differ between the two arms. We will use a random effect to account for the correlation in repeated outcome measures over time within participants. We will also account for correlation in outcome measures by therapist (as participants will be randomized within therapist), by including additional random effects to account for the nesting of patients within therapists. The primary parameter of interest will be a binary indicator for treatment arm assignment. Models will also include a variable for time of measurement. Baseline covariates that are found to be unbalanced between arms may be adjusted for in the model if they were deemed to be potential confounders a priori to adjust for potential confounding and for efficiency gain. We will use all available SF 36 scores on eligible patients from randomization through the last observation. An advantage of the linear mixed effects model is that it is robust to missing outcome measures as long as the missingness mechanism is missing at random (MAR). Patterns of missingness will be assessed carefully and multiple imputation will be used if deemed appropriate. Robust (empirical) standard errors will be used. A p0.05 will be deemed statistically significant but emphasis will be placed on point estimates and confidence intervals. In secondary analysis, we will also include an interaction term between intervention arm and time in order to assess whether the intervention affects the slope of SF 36 scores over time. We may also consider testing interactions between intervention and sex or other important covariates to test if there are differences in the effect of intervention by pre-specified subgroups. We will use a similar approach to evaluate secondary outcomes; however, depending on the distributional form of the secondary outcome, we will use a generalized mixed effects model with the appropriate functional forms for the distribution family and link function.

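### Adjustment is tied to observed baseline imbalance and the amended primary test is unadjusted, giving up precision that the ANCOVA power calculation relied on

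*Combined protocol and SAP*

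**What the plan says.** **Adjustment rule.** The protocol's Analysis Plan, repeated in the Original Statistical Analysis Plan, compares baseline characteristics between arms with t-tests and chi-squared tests. It gives the purpose: "The goal of these comparisons will be to determine if the two arms are balanced on baseline variables after randomization". It then states: "Baseline covariates that are found to be unbalanced between arms may be adjusted for in the model". The same sentence adds a second condition, that the covariate was judged in advance to be a possible confounder, and gives efficiency as one aim of adjusting. There is no list of such covariates and no threshold for imbalance. The model terms that are named are treatment arm, time and random effects; baseline SF-36 is not named as a covariate.

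**Amendment.** Amendments to the Statistical Analysis Plan opens with "Based on covariate balance between the intervention arms, we amended our original statistical analysis plan". It gives a further reason: 69 therapists enrolled, most treating one or two patients. The primary analysis becomes an unadjusted t-test, described as paired, of mean change from baseline to day 60. The mixed model moves to a secondary analysis. The section states that all amendments came before the analyst was unblinded and before outcome data were accessed.

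**Power basis.** Under Accrual: "We used the test for two means in a repeated measures ANCOVA", with a correlation of 0.60 between repeated measures. The target was the "minimum detectable score difference required for over 80% power assuming a type I error rate of 0.05", and "We assumed 50 in each arm".

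**The concern.** In a randomized trial, a significance test on a baseline variable can only pick up chance differences. It says nothing about whether the variable predicts the outcome, and that is what determines how much adjustment helps. A strongly prognostic covariate is worth including when the arms are perfectly balanced; a non-prognostic one is not worth including when they are not. Observed balance is therefore no reason to leave out the baseline value of the outcome.

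The choice also breaks the link with the sample size. The trial was sized on an analysis that removes the variance explained by baseline. If the primary analysis does not do this, the stated power no longer describes it, and a null result would be weaker evidence than the Accrual section suggests.

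**Working it through.** **Inputs (Accrual).** 50 per arm; type I error 0.05, taken as two-sided because the plan does not say; power 80%; r = 0.60; SDs of 10 (MCS), 21.0 (Vitality), 22.7 (Social Functioning), 33.0 (Role-Emotional) and 18 (Mental Health).

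**Step 1: variance per patient, in units of SD².** With equal SDs at baseline and follow-up and one follow-up measure:
- ANCOVA on baseline: 1 − r² = 1 − 0.36 = 0.64
- Unadjusted change score: 2(1 − r) = 2 × 0.40 = 0.80

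**Step 2: reproduce the plan's figures.** Detectable difference = (1.960 + 0.842) × SD × √(variance factor) × √(2/50). For MCS with ANCOVA: 2.802 × 10 × 0.80 × 0.20 = 4.48. For MCS with change: 2.802 × 10 × 0.894 × 0.20 = 5.01.

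| Scale | Stated | ANCOVA (rounded up) | Change (rounded up) |
|---|---|---|---|
| MCS | 5 | 4.48 (5) | 5.01 (6) |
| Vitality | 10 | 9.41 (10) | 10.52 (11) |
| Social Functioning | 11 | 10.18 (11) | 11.38 (12) |
| Role-Emotional | 15 | 14.79 (15) | 16.54 (17) |
| Mental Health | 9 | 8.07 (9) | 9.02 (10) |

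ANCOVA rounded up matches all five. The change score does not: even with rounding to the nearest point it misses Vitality (11) and Role-Emotional (17). Two other forms were tried and also fail: follow-up score alone (5.60 for MCS, 18.49 for Role-Emotional) and ANCOVA on the mean of two follow-ups (3.72 and 12.27).

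**Step 3: power at the stated differences, 50 per arm.** The noncentral t has noncentrality difference / (SD × √factor × 0.20), with 97 degrees of freedom for ANCOVA and 98 for change.

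| Scale | ANCOVA | Unadjusted change |
|---|---|---|
| MCS | 87.2% | 79.0% |
| Vitality | 83.8% | 75.0% |
| Social Functioning | 85.0% | 76.5% |
| Role-Emotional | 80.3% | 71.1% |
| Mental Health | 87.2% | 79.0% |

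The normal approximation gives 79.8, 75.9, 77.3, 71.9 and 79.8% for the change score, also below 80% throughout. The enrolment target leaves 115 × 0.85 = 97.75 patients, about 49 per arm, so 50 per arm is not pessimistic.

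**Step 4: size of the loss.** Variance ratio 0.80/0.64 = 1.25; standard error ratio √1.25 = 1.118. Fifty per arm under the change score is worth 50/1.25 = 40 per arm under ANCOVA. In general the ratio is 2(1 − r)/(1 − r²) = 2/(1 + r): 1.43 at r = 0.4 and 1.11 at r = 0.8.

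**Step 5: what a chance imbalance does.** A change score subtracts baseline with slope 1, where the plan's correlation implies 0.6. A 0.2 SD imbalance is 2 MCS points and shifts the estimated difference by (0.6 − 1) × 2 = −0.8 points. At 50 per arm, 0.2 SD is one standard error of the baseline difference (√(2/50) = 0.2), so a 0.05 test would not flag it. The largest difference that such a test passes is about 1.96 × 0.2 = 0.39 SD, or 3.9 MCS points.

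**Step 6: type I error.** In 20,000 simulated null trials at r = 0.60, the change score and ANCOVA each rejected in 4.9%.

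**The case against.** Several points on the other side are sound and limit the finding.

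- **Baseline tests are not the only gate.** A covariate must also have been judged a possible confounder in advance, so it would be wrong to say that significance tests alone decide. But with no list, no threshold and permissive wording, the decision still turns on the observed baseline data.
- **Balance was not the only reason for the amendment.** Very small therapist clusters were the other. They are an argument about therapist random effects and have no bearing on adjusting for baseline.
- **The timing is stated.** A reader might infer an outcome-driven change or an inflated false-positive rate. The documents support neither: the amendments are said to precede unblinding and outcome access, and the unadjusted test keeps its type I error.
- **The change score does use baseline SF-36.** A reader might conclude that chance imbalance goes uncorrected. For SF-36 it is over-corrected; only other prognostic covariates go uncorrected. Nor is the 0.8-point shift a second harm: averaged over randomizations the comparison is unbiased, and such shifts are already part of the extra variance.
- **Baseline SF-36 is not said to fall under the imbalance rule.** That would be an inference. What can be said is that no section names it as a covariate.
- **The mixed model reportedly gave almost the same answer.** This is some reassurance, but the amendment does not say whether that model contained any baseline covariate, so no baseline-adjusted result is shown.
- **The loss is slight on some scales.** For MCS and Mental Health, power is 79.0%. It is 71.1% to 76.5% on the other three.

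**Conclusion.** The point holds as one about precision and about consistency with the power calculation. Making adjustment depend on observed imbalance, and citing balance in support of an unadjusted primary test, rests on the wrong criterion. At the plan's own correlation it adds 25% to the variance and puts power below the stated 80% on all five scales, by about 1 percentage point on MCS and Mental Health and about 9 on Role-Emotional.

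This assumes a two-sided 0.05 test, equal SDs at both times, a single follow-up measure, r = 0.60 and no therapist clustering. It also reads the paired t-test as a two-sample test of changes, since a paired test does not compare two independent arms. The direction of the loss does not depend on r (the ratio 2/(1 + r) exceeds 1 for any r below 1), but its size does.

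The documents do not show that the reported conclusions are wrong.

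**What to change.** **In the plan.** Remove the baseline significance tests and the imbalance trigger, and keep the baseline table descriptive. Include baseline SF-36 as a fixed covariate in the day-60 model whatever the observed balance. Do the same for each secondary outcome that has a baseline value, and name any other covariates in a list.

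**In the report.** Because the amendment section already describes results, the adjusted model cannot now be presented as the planned primary analysis. Show the baseline-adjusted SF-36 estimate and confidence interval beside the amended primary analysis, labelled as added after the results. Failing that, restate the power for the unadjusted change-score test, using the figures above or the sponsor's own. State also whether the secondary mixed model included any baseline covariate.

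**Cost.** One further model per outcome and a few sentences. No new SF-36 data are needed: the baseline survey precedes randomization (Method for Assigning Subjects to Groups), and the amended analysis already uses change from baseline. The available text does not list the survey's instruments, so baseline values for the secondary outcomes need confirming.
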